2.3 RISK/BENEFIT ASSESSMENT

2.3.1 KNOWN POTENTIAL RISKS

Blood Sampling: Blood samples should pose minimal health risks to participants. Every attempt will be made to obtain blood from the enrolled infant at the time that routine samples are collected for clinical indications. For the infant, a minimum of two and a maximum of five dried blood spots are needed for NewbornDx, a total blood volume of 1mL for rWGS. This one-time blood sample from the infant should not cause undue trauma or excessive blood loss. If the clinical team does not feel it is safe to obtain the sample from the infant, then we will obtain the blood just prior to a packed red blood cell transfusion. The 3ml of blood from each biological parent is considered minimal for an adult. Risks associated with blood draws are usually minor and include pain, anxiety, bleeding, bruising, fainting, and rarely infection at the site. All samples will be collected by qualified staff following hospital guidelines and standard precautions.

Loss of confidentiality: Since we are storing identifying information about the infant and parents, there is a small risk that this information may be compromised. All study related material will be stored securely. Each enrolled infant will be assigned a unique study identification number which does not include any identifiers. Infant information entered into the password-protected REDCap System and documents used for remote monitoring will be identified by the study ID number. Each site will keep the link between the study ID number and identifiers for all subjects enrolled at their site in a secure password-protected spreadsheet. Blood samples, medical information provided on the laboratory requisition form, sequencing data, and results from the laboratory will be identifiable by name and date of birth. This is to ensure that: 1) the correct infant can be identified immediately 24/7 in the case of a time sensitive result that could influence

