5.2 EXCLUSION CRITERIA

An individual who meets any of the following criteria will be excluded from participation in this study:

1. A known genetic diagnosis (e.g. prenatal testing, biochemical testing and/or enzyme analysis)
2. Major congenital anomaly (renal, cardiac, hepatic, neurologic, or pulmonary malformations) associated with a chromosomal anomaly detected on prenatal testing (e.g. ultrasound, genetic testing)
3. Presence of documented congenital infection (e.g. congenital cytomegalovirus)
4. Infants considered non-viable due to prematurity (< 23 0/7 weeks GA)
5. Infants who are not expected to receive medical care in the US healthcare system from time of discharge home until 1 year CGA

Lack of participation by one or both biological parents in the trio analysis does not preclude the infant from participating in this study. This situation could occur if a biological parent does not provide consent for his/her own blood sample to be used for a trio analysis, if a blood sample cannot be obtained, or in the case of an egg or sperm donor.

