8.2 ENROLLMENT

PI Assessment of whether or not an infant requires urgent testing

This protocol will prioritize testing of infants who are severely ill. Infants with the following conditions may qualify for the most rapid testing possible:

- Infant requires mechanical ventilation
- Infant is exhibiting severe neurological complications (i.e. uncontrolled seizures)
- Infant is hemodynamically unstable
- Site PI selects this option at his/her discretion

There is not a specific timeframe in which urgent testing must be returned; rather, the laboratory does its best to expedite testing. Refer to the “MOP about how to notify laboratories of urgent testing.

Enrollment in REDCap System

Complete the enrollment and urgent testing eCRFs in REDCap. The Infant Study ID and linking infant identifiers will be added to the secure site master enrollment log. The Infant Study ID will be used for all data entered into REDCap and in study files.

Ordering of Laboratory Tests, Collection and Shipment of Blood Samples

Three laboratories are involved in this protocol: Athena (Quest), RCIGM and Sema4.

1. Athena Diagnostics (a subsidiary of Quest Diagnostics) is performing the NewbornDx panel (infant and when available, the biological parents) and confirmation testing for pathogenic, likely pathogenic and suspicious VUS findings.
2. RCIGM is performing rWGS (infant and when available, the biological parents) and confirmation testing for pathogenic, likely pathogenic and suspicious VUS.
3. In some circumstances, Sema4 will be involved with DNA extraction and confirmation testing only for infants enrolled at Mount Sinai (refer to section 6.1.1).

Blood Sample Collection

Blood samples are collected as follows:

Who	Samples to Collect
Infant	
 • A minimum of two and maximum of five fully saturated dried blood spots (DBS) using study-provided Perkin Elmer 226 filter paper* • Two 0.5ml blood samples in study-provided EDTA tubes (one 0.5ml sample is acceptable, but two are preferred)
Mother	
 • Two 0.5ml blood samples in study-provided EDTA tubes (one 0.5ml sample is acceptable, but two are preferred) • One 2mL blood sample in a study-provided EDTA tube
Father	
 • Two 0.5ml blood samples in study-provided EDTA tubes (one 0.5ml sample is acceptable, but two are preferred) • One 2mL blood sample in a study-provided EDTA tube

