*In circumstances in which an infant meets urgent criteria and where allowing the required 3-hour timeframe for a blood spot card to dry prior to shipping may adversely affect time to diagnosis and potential life-saving treatment, 1ml of whole blood in an EDTA tube may be obtained in lieu of the blood spot card and sent to Athena.

Refer to the MOP for detailed instructions about the timing and source of blood samples, collection procedures and documentation of the date/time of blood collection. If possible, collect blood from the infant at the time of routine clinical testing to minimize discomfort. If the clinical team does not feel it is safe to withdraw 1ml of blood from the infant, wait until just prior to the time a packed red blood cell transfusion is administered.

All blood samples will be obtained by qualified staff following the hospital guidelines and standard precautions. DNA extracted and held prior to enrollment may be used for this study (i.e. the clinical team obtained a sample prior to putting an infant on ECMO knowing an untainted sample may be needed later for clinical purposes).

Obtain whole blood samples from each biological parent near the time the samples are being collected from the infant. In the case of an assay failure or a damaged sample, an additional blood sample for the infant or a biological parent may be obtained and shipped to the laboratory.

Labeling of Blood Samples

Each sample should be labeled with name, date of birth and/or MRN, and sample ID number using permanent ink. Label each sample with name and date of birth and/or MRN at the time of sample collection. Add the sample ID number for each sample after you complete the laboratory requisition forms. The sample ID numbers for rWGS are generated by the RCIGM ordering portal at the time the online requisition is completed. The sample ID numbers for NewbornDx will be generated manually by the site as instructed in the MOP.

Blood Sample Storage Conditions until Shipment

Keep the blood samples refrigerated at 4°C until the time of shipment (up to 5 days). Do not freeze. The DBS may be kept at room temperature until shipment.

Order NewbornDx and rWGS

Complete the requisitions for each laboratory as follows and according to the MOP:

The site shipping samples	Requisitions to complete	Process

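### The 1 mL safe-to-draw check in section 8.2 does not match the optional urgent draw, which takes 2.0 mL of infant whole blood (1.5 mL with one rWGS tube)

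*Combined protocol and SAP*

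**What the plan says.** The blood collection table in section 8.2 sets the default infant draw. Athena receives two to five dried blood spots for NewbornDx. The rWGS sample is "Two 0.5ml blood samples in study-provided EDTA tubes (one 0.5ml sample is acceptable, but two are preferred". The shipping table in the same section sends the spots to Athena and the rWGS tubes to RCIGM (to Sema4 for Mount Sinai).

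A footnote to the collection table adds an option for an infant who meets the urgent criteria, in circumstances "where allowing the required 3-hour timeframe for a blood spot card to dry prior to shipping may adversely affect time to diagnosis". The same condition also names the effect on treatment that could save the infant's life. In that case "1ml of whole blood in an EDTA tube may be obtained in lieu of the blood spot card and sent to Athena". Both conditions must hold, and the substitution is permitted, not required.

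The next paragraph gives the safety check: "If the clinical team does not feel it is safe to withdraw 1ml of blood from the infant", the site waits until just before a packed red cell transfusion.

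Section 2.3.1 describes the infant sample as "a minimum of two and a maximum of five dried blood spots are needed for NewbornDx, a total blood volume of 1mL for rWGS". It does not mention the urgent option. Its own safeguard names no volume: "If the clinical team does not feel it is safe to obtain the sample from the infant", blood is taken just before a transfusion.

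**The concern.** The only safety check that names a volume gives a figure that is right for one component of the default draw and too low for the urgent route. A team that reads it literally considers 1 mL and may then collect up to 2 mL.

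The infants on this route are the sickest in the trial. Among the urgent criteria in section 8.2 is "Infant requires mechanical ventilation", and hemodynamic instability is another. Section 5.2 excludes on prematurity only "Infants considered non-viable due to prematurity (< 23 0/7 weeks GA" and sets no minimum weight, so a very small infant can qualify. Section 2.3.3 names anemia as a risk of drawing blood. Section 8.4.3.3 judges whether an adverse event was expected against the risk information in the protocol. The risk text should therefore describe the largest draw that the protocol allows.

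What is at stake is the accuracy of a safety instruction and of the risk description. No estimate or analysis depends on it.

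**Working it through.** **The plan's own figures.** The rWGS volume in 2.3.1 is 2 × 0.5 mL = 1.0 mL, which reproduces the stated 1 mL exactly. The parent volume in 2.3.1 also reproduces: 2 × 0.5 + 2.0 = 3.0 mL. So the 1 mL in the check equals the rWGS tubes alone and already leaves out the spots. If a reader takes it instead as the Athena tube in the footnote, it is still one component and not the sum.

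**Whole blood by route** (volumes from section 8.2). The two samples go to different laboratories, so they add.

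| Route | Athena | rWGS | Whole blood | Figure in the check |
|---|---|---|---|---|
| Default, two tubes | spots | 1.0 mL | 1.0 mL plus spots | 1 mL |
| Default, one tube | spots | 0.5 mL | 0.5 mL plus spots | 1 mL |
| Urgent option, two tubes | 1.0 mL | 1.0 mL | 2.0 mL | 1 mL |
| Urgent option, one tube | 1.0 mL | 0.5 mL | 1.5 mL | 1 mL |

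The urgent route takes 2.0 or 1.5 times the volume named in the check. These totals are for one initial collection; section 8.2 allows a further sample after an assay failure or damage.

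**Net increase over the default draw.** The documents give no volume for a spot. Assume 0.03 to 0.1 mL each.

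- Replaced spots: 2 × 0.03 = 0.06 mL to 5 × 0.1 = 0.5 mL.
- Same number of rWGS tubes on both routes: 1.0 − 0.5 = 0.50 mL to 1.0 − 0.06 = 0.94 mL.
- Number of tubes allowed to differ, smallest case: default 1.0 + 0.5 = 1.5 mL against urgent 0.5 + 1.0 = 1.5 mL, an increase of zero.
- Number of tubes allowed to differ, largest case: default 0.5 + 0.06 = 0.56 mL against urgent 2.0 mL, an increase of 1.44 mL.

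**Share of blood volume.** Share = volume ÷ (weight × mL/kg). Weights and 80–90 mL/kg are assumptions. The net column uses 0.50 mL at 90 mL/kg to 0.94 mL at 80 mL/kg, with the number of tubes held constant.

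| Weight | Full 2.0 mL | Net 0.50–0.94 mL |
|---|---|---|
| 0.5 kg | 4.44–5.00% | 1.11–2.35% |
| 1 kg | 2.22–2.50% | 0.56–1.18% |
| 3 kg | 0.74–0.83% | 0.19–0.39% |
| 10 kg | 0.22–0.25% | 0.06–0.12% |

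For example, at 0.5 kg: 2.0 ÷ (0.5 × 90) = 4.44% and 2.0 ÷ (0.5 × 80) = 5.00%. The full 2.0 mL includes blood that the default draw takes anyway, so the net column is the fairer measure of the option.

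**The case against.** The case for leaving the text alone is substantial. The 2.3.1 safeguard names no volume and covers a 2 mL draw as it stands. The 8.2 sentence asks for clinical judgement and does not stop a team from judging 2 mL unsafe. The footnote sits directly above the check and every tube volume is given, so a team would have to choose the extra tube and then overlook the sum. Qualified staff draw under hospital guidelines, previously extracted DNA may be used, and 7.2 lists unsafe collection as a reason for withdrawal. Harm from sampling is reportable under 8.4.1. Detailed collection instructions are in the MOP, which was not seen and may already give the total. All of this stands, and it keeps the likely harm small. None of it makes 1 mL the right figure for the urgent route.

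A second objection concerns the remedy. The only action tied to the check is to wait for a transfusion. Raising the figure alone would send a team that finds 2 mL unsafe to that wait, when the spot card costs only its 3-hour drying time. This is correct, and the fix has to name the fallback.

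A reader might infer more: that the protocol breaches its own 1 mL limit, or exposes infants to unsafe blood loss. The documents do not support either. The 1 mL figure is a prompt for judgement and not a cap. No maximum safe volume is stated, so nothing here shows that 2 mL is excessive at any weight. The documents give neither a weight distribution nor how often the option is used.

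**Conclusion.** The point holds as a minor safety-wording correction. On the urgent substitution route infant whole blood is 2.0 mL, or 1.5 mL with one rWGS tube. The 8.2 check names 1 mL, and 2.3.1 omits the option. These totals follow from the protocol text alone and need no assumption.

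The clinical size is small and uncertain. Every percentage above rests on assumed weights, mL/kg and spot volumes, and against the largest permitted default draw the increase can be zero. The mismatch matters mainly for very small urgent infants. Whether it survives in practice depends on the MOP and the consent form, neither of which was available.

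**What to change.** - In 8.2, make the check refer to the total research volume planned for that infant: 1 mL plus spots by default, up to 2 mL with the urgent option.
- Add the fallback: if the larger urgent draw is judged unsafe, first revert to the spot card, a single 0.5 mL rWGS tube, or both. Wait for a transfusion only if that is also unsafe.
- In 2.3.1, mention the urgent option and state the 2 mL maximum.
- Confirm that the MOP and consent form agree.

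The cost is wording in two sections, IRB review of the change and a check of the two other documents. If the consent form states a volume, its English and Spanish versions need revision. A few urgent teams may decline the substitution and accept the 3-hour drying time.

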8.3 SAFETY AND OTHER ASSESSMENTS

Enrolling sites must actively monitor, identify and assess adverse events (AE) in the study. Identification of AEs will be based on review of the medical record, observation by study staff and by report during the parent survey/interviews. For each AE, the investigator will determine whether the adverse event is serious, provide the duration (start and end dates), the severity grade (mild, moderate, severe), the relationship to the study testing (unlikely, possibly, and probably), action(s) taken, and the outcome. The AE assessment must be documented and retained with study files. The Investigator's signature and date on the source document that supports the causality noted on the AE form ensures that a medically qualified assessment of causality was done.

The laboratories conducting genetic sequencing for this study fall under the CLIA/CAP regulations. They continually monitor for errors and non-conforming events and will notify the study-wide PIs via phone/email of an error/event that affected a result for the infant. They will also notify the study-wide PIs if a data breach were to occur. In these instances, the study-wide PI would file an adverse event, and notify the DSMB, IRB, and NCATS as required. The laboratories are not expected to report adverse events as described in sections 8.3 and 8.4.

8.4 ADVERSE EVENTS AND SERIOUS ADVERSE EVENTS

8.4.1 DEFINITION OF ADVERSE EVENTS (AE)

An Adverse Event for this study will only include the following:

- An untoward medical occurrence related to obtaining the study blood samples
- If findings for the infant thought to be secondary at the time results are reported are given to the research team, clinician or parent/guardian when the parent/guardian did not opt-in to receive secondary findings for their infant
- If secondary findings for a parent are reported to the research team, clinician or parent when the parent did not opt-in to receive parental secondary findings
- Intervention based on inaccurate result returned (testing error; provisional result not confirmed)
- Intervention based on wrong result returned (human error, result not accurately matched up with the correct infant)
- Untoward event related to an intervention initiated due to the genomic testing results (intervention that would not have been initiated without the genomic testing results)
- Loss of confidentiality related to study participation

- Any new untoward medical occurrence related to study participation or the genetic sequencing results
- A pre-existing condition that worsens in terms of frequency or intensity and the worsening is due to study participation/genetic sequencing results
- The infant dies due to error because the infant was enrolled in this study (erroneous result or misidentification)

Events not reported as Adverse Events for this study:

- A pre-existing condition at the time of enrollment
- A pre-existing condition that worsens in terms of frequency or intensity but the worsening is not related to study participation/genetic sequencing
- A new untoward medical occurrence that is not related to study participation/genetic sequencing results and does not result in death
- Death due to natural causes before genetic testing results are returned (i.e. prematurity)
- Death due to parent/guardian wishes to withdraw life sustaining treatment if an infant is determined to have a lethal condition by genetic testing

8.4.2 DEFINITION OF SERIOUS ADVERSE EVENTS (SAE)

An adverse event (AE) or suspected adverse reaction is considered "serious" if in the view of either the investigator or sponsor, it results in any of the following outcomes: death, a life-threatening adverse event, prolongation of existing hospitalization, a persistent or significant incapacity or substantial disruption of the ability to conduct normal life functions, or a congenital anomaly/birth defect. Important medical events that may not result in death, be life-threatening, or require more prolonged hospitalization may be considered serious when they may jeopardize the infant and require medical or surgical intervention to prevent one of the outcomes listed in this definition.

Events that are not related to study participation or genomic sequencing will not be captured as an SAE since the definition of an adverse event for this study requires a relation to genetic testing (rather than the underlying disorder).

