Following transfer of facility or discharge home, study staff will contact one parent/guardian monthly to assess how the infant is progressing until 1 year CGA. The parent/guardian will be asked about any new testing, diagnosis, medications, medical visits or hospitalizations, and any missed days of work due to their child's disorder. Ideally, the parent will receive a link via email to complete the monthly parent survey online in the REDCap system; however, the parent/guardian may be contacted by e-mail or phone per the parent/guardian's preference. Self-reported QoL information will be collected from a parent/guardian at 3-month intervals to infer the impact on the family of any prolonged illness. The follow-up surveys will be translated into Spanish. In the case of a parent/guardian who does not read English or Spanish, the follow-up contact will need to be made with an interpreter by phone. Upon request by the health

economics analysts and as permitted in the ICF, medical records and billing information from any hospitalizations and any outpatient health care utilization may be obtained from the provider institutions to complement parent/guardian self-report.

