8.4.4 TIME PERIOD AND FREQUENCY FOR EVENT ASSESSMENT AND FOLLOW-UP

AEs must be actively identified from the signing of the ICF until the infant reaches one year CGA. AEs must be followed until an outcome is known. All events that cannot be resolved by 30 days after the final assessment at 1 year CGA will be considered resolved by convention and entered in the REDCap system.

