8.4.5 ADVERSE EVENT REPORTING

Reporting of non-serious AEs must occur using the Adverse Event eCRF in the REDCap system according to the following:

Event	Timeframe for Site to Report	Timeframe for Study PI to Report
AE, not serious	Site enters AE into EDC within 7 business days of identification.	The study PI reports to the DSMB every 6 months and in the annual progress report to NCATS.

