8.4.6 SERIOUS ADVERSE EVENT REPORTING

Reporting of SAEs must occur using the adverse event eCRF in the REDCap system according to the following:

Event	Timeframe for Site to Report	Timeframe for Study-wide PI to Report
SAE	Site reports to the study-wide PI within 24 hours of learning about the event.	The study-wide PI will alert the DSMB chair within 24 hours of learning about the event. If the SAE is also an unanticipated problem, the study-wide PI will also report to the central IRB and NCATS within 24 hours of learning about the event.

To ensure accurate clinical trial reporting and correct interpretation of safety signals, each death will be examined to determine cause. This may be difficult in the preterm infant population as there are often multiple events which contribute to death. For the

purposes of this clinical trial, the investigator will attribute the cause of death to the AE which had the greatest medical contribution to death, regardless of whether or not the event was the most proximal. For example, if an infant has a large intraventricular hemorrhage that leads to seizures and death, the death should be attributed to intraventricular hemorrhage, not seizures. The investigator should utilize all available information when attributing cause of death. Autopsy information should be utilized where available to amend the adverse event report if needed. It is recognized that the death certificate may not reflect clinical trial procedures and thus may not match the cause of death attributed by the investigator. In the rare situation for deaths in which no single AE represents the greatest medical contribution to death, the adverse event is listed as “Death not associated with an AE term” and one of the following causes must be selected: 1) death not otherwise specified (i.e. failure to thrive), 2) extreme prematurity, 3) multi-organ failure, and 4) sudden death (no documentation of cause, includes Sudden Infant Death Syndrome). For cases in which the cause of death is unclear, the final determination as to which AE or organ system the death should be attributed will be determined by the DSMB.

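### A study-related readmission is not serious on the ground of hospitalization alone, although adverse events are followed after discharge to 1 year CGA

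*Combined protocol and SAP*

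**What the plan says.** Section 8.4.2 lists the outcomes that make an adverse event serious: "death, a life-threatening adverse event, prolongation of existing hospitalization, a persistent or significant incapacity", then substantial disruption of normal functioning, and congenital anomaly. It adds a clause for other cases: "Important medical events that may not result in death, be life-threatening, or require more prolonged hospitalization may be considered serious when they may jeopardize". Under that clause it is the infant who must be at risk, and the event must also "require medical or surgical intervention to prevent one of the outcomes listed in this definition". The seriousness call belongs to either the investigator or the sponsor. Events unrelated to study participation or sequencing are not SAEs.

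On timing, Section 8.4.4 states: "AEs must be actively identified from the signing of the ICF until the infant reaches one year CGA". Section 8.2 provides for monthly parent contact after transfer or discharge, at which "The parent/guardian will be asked about any new testing, diagnosis, medications, medical visits or hospitalizations", among other things. It also allows for results being returned after the infant has gone home.

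The reporting routes differ by seriousness. For a non-serious event, Section 8.4.5 says: "Site enters AE into EDC within 7 business days of identification", and then: "The study PI reports to the DSMB every 6 months and in the annual progress report to NCATS". For a serious event, Section 8.4.6 says: "Site reports to the study-wide PI within 24 hours of learning about the event", and the study-wide PI then has 24 hours to alert the DSMB chair.

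**The concern.** The hospitalization criterion fits an infant who is still an inpatient, but the adverse event window does not end at discharge. Section 8.4.1 counts as adverse events an untoward event from an intervention begun because of a sequencing result, and an intervention based on an inaccurate or wrong result. Either can lead to an admission from home. Section 8.4.2 has no rule that makes such an admission serious.

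The speed and consistency of safety reporting are at stake. Two sites could see similar study-related readmissions and send one by the 24-hour route and the other by the routine route, depending on how each applies the discretionary clause. Section 10.1.2 names inaccurate test results as a possible reason to stop the trial, so an admission caused by such a result is something the DSMB would want to know promptly.

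**Working it through.** No rate, sample size or power figure enters this point. The check is a comparison of the definition, the follow-up window and the reporting routes.

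1. **Is new hospitalization listed anywhere?** Section 8.4.2 lists only the prolongation of a current stay. Sections 8.3, 8.4.1 and 8.4.3 to 8.4.6 do not add a new admission or readmission.

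2. **Can the gap arise during planned follow-up?** Yes. Adverse events are sought to 1 year CGA (8.4.4), parents are asked monthly about hospitalizations (8.2), and results can be returned after discharge (8.2), so an intervention prompted by a result can start at home.

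3. **Does the important-medical-event clause close it?** Not reliably. It is permissive. It also requires that the intervention prevent an outcome on the list, and a new admission is not on the list. It speaks only of jeopardy to the infant. Biological parents are research subjects under the definitions, and Section 8.4.3.1 grades their events too, but the clause does not reach them.

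4. **Which routes can a study-related readmission take?**

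| Status of the event | Site's time limit | Time to the DSMB |
|---|---|---|
| Serious by another listed criterion or by judgement (8.4.6) | 24 hours to the study-wide PI | Chair within a further 24 hours, so 24 + 24 = 48 hours from the site learning of it |
| Not serious, but an unanticipated problem (8.5.2) | 8 working days | Chair within 10 working days of discovery |
| Neither (8.4.5) | 7 business days to the database | Routine report every 6 months |

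Seven business days span at least one weekend, so the limit is at least 7 + 2 = 9 calendar days. Only the second and third rows miss the 24-hour report.

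5. **Is the second row a dependable fallback?** It requires the event to be unexpected (8.5.1). Section 8.4.3.3 judges expectedness against the risks described in the protocol, and Section 2.3.3 already lists unnecessary therapy begun on an unconfirmed diagnosis. A readmission through that mechanism could be judged expected and fall to the third row.

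6. **Do the laboratory routes cover it?** Under Section 8.3 the laboratories notify the study-wide PIs of an error that affected an infant's result. Under Section 8.2 they telephone when a final result may have immediate implications, for example when a provisional result is not confirmed. Both report the result error. Neither reports the admission that followed, and neither covers harm from an intervention based on a correct result.

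All of these time limits start when the site or laboratory learns of the event. With monthly parent contact, a readmission elsewhere may come to light some weeks later whichever route applies.

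**The case against.** The strongest reply is that the protocol already has several ways to bring an important readmission forward. A readmission that is life-threatening, causes significant incapacity or seriously disrupts normal functioning is an SAE as the text stands. The important-medical-event clause expressly reaches events that do not prolong a stay, and either the investigator or the sponsor can invoke it. Many related readmissions that matter would plausibly qualify. Judgement is not peculiar to that clause, since the whole definition rests on the view of the investigator or sponsor. Wrong results have their own laboratory notification, and intervention on one is an adverse event whether or not the infant is readmitted. The study is descriptive, adverse events are confined to study-related ones, and no estimate changes.

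Much of this stands, and it rules out four stronger readings that a reader might infer:

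- **Such readmissions always escape 24-hour reporting.** They do not; the other criteria and the discretionary clause still apply.
- **Most adverse event time falls after discharge.** The documents give no expected length of stay or age at enrollment, and every infant is an inpatient when enrolled, so the split is unknown.
- **Six months is the usual delay to the DSMB.** It is roughly the outer bound, for an event that is neither serious nor an unanticipated problem.
- **Erroneous results themselves would go undetected.** Detection does not depend on the SAE definition.

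The reply does not supply a rule for the remaining case: a related admission from home that meets no other criterion and that nobody judges important.

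**Conclusion.** The point holds in limited form. As written, a study-related new admission or readmission is not serious because of the hospitalization. If no other criterion or judgement makes it serious, the site's limit is 7 business days or 8 working days instead of 24 hours. The DSMB then learns of it within 10 working days at best, or otherwise at the next 6-monthly report, instead of within 48 hours.

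This rests on reading 8.4.2 literally and on the manual of procedures and the data and safety monitoring plan, which are not among the documents, not adding the criterion. How often such events would occur cannot be estimated from the documents. The omission affects the timeliness and consistency of safety reporting and no endpoint. It may be deliberate, but no reason is given.

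**What to change.** Amend Section 8.4.2 so that the hospitalization criterion covers new inpatient hospitalization, including readmission, as well as prolongation of a current stay. Make the matching change in the important-medical-event clause, which at present also speaks only of a prolonged stay. Keep the study-relatedness requirement, so that admissions due to the underlying disorder stay outside SAE reporting. State that the criterion applies throughout the Section 8.4.4 window, and say whether it also applies to biological parents. If the omission is intended, say so and give the reason.

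The cost is a few words in a protocol amendment, a note to sites, and probably a small number of extra expedited reports. No analysis or sample size changes.
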